5.2.1.2 Dose Modification

Adverse events (both non-serious and serious) associated with pembrolizumab exposure may represent an immunologic etiology. These adverse events may occur shortly after the first dose or several months after the last dose of treatment. Pembrolizumab must be withheld for drug-related toxicities and severe or life-threatening AEs as per Table 3 below. See Section 5.6.1 and Events of Clinical Interest Guidance Document for supportive care guidelines, including use of corticosteroids.

Table 3

Dose Modification Guidelines for Drug-Related Adverse Events

Toxicity	Hold Treatment For Grade	Timing for Restarting Treatment	Discontinue Subject
Diarrhea/Colitis	2-3	Toxicity resolves to Grade 0-1.	Toxicity does not resolve within 12 weeks of last dose or inability to reduce corticosteroid to 10 mg or less of prednisone or equivalent per day within 12 weeks.
	4	Permanently discontinue	Permanently discontinue
AST, ALT, or	2	Toxicity resolves to Grade 0-1	Toxicity does not resolve within 12 weeks of last dose.
Increased Bilirubin	3-4	Permanently discontinue (see exception below) ¹	Permanently discontinue
Type 1 diabetes mellitus (if new onset) or	T1DM or 3-4	Hold pembrolizumab for new onset Type 1 diabetes mellitus or Grade 3-4 hyperglycemia associated with evidence of	Resume pembrolizumab when patients are clinically and metabolically stable.

NCT02882282

Toxicity	Hold Treatment For Grade	Timing for Restarting Treatment	Discontinue Subject							
Hyperglycemia		beta cell failure.								
Hypophysitis	2-3	Toxicity resolves to Grade 0-1	Toxicity does not resolve within 12 weeks of last dose or inability to reduce corticosteroid to 10 mg or less of prednisone or equivalent per day within 12 weeks.							
	4	Permanently discontinue	Permanently discontinue							
Hyperthyroidism	3	Toxicity resolves to Grade 0-1	Toxicity does not resolve within 12 weeks of last dose or inability to reduce corticosteroid to 10 mg or less of prednisone or equivalent per day within 12 weeks.							
	4	Permanently discontinue	Permanently discontinue							
Hypothyroidism	2-4	Therapy with pembrolizumab can be continued while treatment for the thyroid disorder is instituted	Therapy with pembrolizumab can be continued while treatment for the thyroid disorder is instituted.							
Infusion Reaction	3-4	Permanently discontinue	Permanently discontinue							

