5.6 Rescue Medications & Supportive Care

5.6.1 Supportive Care Guidelines

Subjects should receive appropriate supportive care measures as deemed necessary by the treating investigator. Suggested supportive care measures for the management of adverse events with potential immunologic etiology are outlined below and in greater detail in the ECI guidance document. Where appropriate, these guidelines include the use of oral or intravenous treatment with corticosteroids as well as additional anti-inflammatory agents if symptoms do not improve with administration of corticosteroids. Note that several courses of steroid tapering may be necessary as symptoms may worsen when the steroid dose is decreased. For each disorder, attempts should be made to rule out other causes such as metastatic disease or bacterial or viral infection, which might require additional supportive care. The treatment guidelines are intended to be applied when the investigator determines the events to be related to pembrolizumab.

Note: if after the evaluation the event is determined not to be related, the investigator is instructed to follow the ECI reporting guidance but does not need to follow the treatment guidance (as outlined in the ECI guidance document). Refer to Section 5.2.1 for dose modification.

It may be necessary to perform conditional procedures such as bronchoscopy, endoscopy, or skin photography as part of evaluation of the event. Suggested conditional procedures, as appropriate, can be found in the ECI guidance document.

• Pneumonitis:

- o For **Grade 2 events**, treat with systemic corticosteroids. When symptoms improve to Grade 1 or less, steroid taper should be started and continued over no less than 4 weeks.
- o For **Grade 3-4 events**, immediately treat with intravenous steroids. Administer additional anti-inflammatory measures, as needed.
- o Add prophylactic antibiotics for opportunistic infections in the case of prolonged steroid administration.

• Diarrhea/Colitis:

Subjects should be carefully monitored for signs and symptoms of enterocolitis (such as diarrhea, abdominal pain, blood or mucus in stool, with or without fever) and of bowel perforation (such as peritoneal signs and ileus).

NCT02882282

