- All subjects who experience diarrhea/colitis should be advised to drink liberal quantities of clear fluids. If sufficient oral fluid intake is not feasible, fluid and electrolytes should be substituted via IV infusion. For Grade 2 or higher diarrhea, consider GI consultation and endoscopy to confirm or rule out colitis.
- o For **Grade 2 diarrhea/colitis** that persists greater than 3 days, administer oral corticosteroids.
- o For **Grade 3 or 4 diarrhea/colitis** that persists > 1 week, treat with intravenous steroids followed by high dose oral steroids.
- When symptoms improve to Grade 1 or less, steroid taper should be started and continued over no less than 4 weeks.
- Type 1 diabetes mellitus (if new onset, including diabetic ketoacidosis [DKA]) or ≥ Grade 3 Hyperglycemia, if associated with ketosis (ketonuria) or metabolic acidosis (DKA)
 - o For **T1DM** or **Grade 3-4** Hyperglycemia
 - Insulin replacement therapy is recommended for Type I diabetes mellitus and for Grade 3-4 hyperglycemia associated with metabolic acidosis or ketonuria.
 - Evaluate patients with serum glucose and a metabolic panel, urine ketones, glycosylated hemoglobin, and C-peptide.

• Hypophysitis:

- For Grade 2 events, treat with corticosteroids. When symptoms improve to Grade 1 or less, steroid taper should be started and continued over no less than 4 weeks. Replacement of appropriate hormones may be required as the steroid dose is tapered.
- o For **Grade 3-4** events, treat with an initial dose of IV corticosteroids followed by oral corticosteroids. When symptoms improve to Grade 1 or less, steroid taper should be started and continued over no less than 4 weeks. Replacement of appropriate hormones may be required as the steroid dose is tapered.

• Hyperthyroidism or Hypothyroidism:

Thyroid disorders can occur at any time during treatment. Monitor patients for changes in thyroid function (at the start of treatment, periodically during treatment, and as indicated based on clinical evaluation) and for clinical signs and symptoms of thyroid disorders.

- o Grade 2 hyperthyroidism events (and Grade 2-4 hypothyroidism):
 - In hyperthyroidism, non-selective beta-blockers (e.g. propranolol) are suggested as initial therapy.

NCT02882282

• In hypothyroidism, thyroid hormone replacement therapy, with levothyroxine or liothyroinine, is indicated per standard of care.

o **Grade 3-4** hyperthyroidism

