6.1 TRIAL FLOW CHART

6.2 Study Flow Chart

Trial Period:	Screening Phase		reatment Follow-Up Cycles ^a									Long-Term Follow-Up			
Treatment Cycle/Title:	Pre- screening (Visit 1)	Main Study Screening (Visit 2)	1	2	3	4	End of Treatment / Re-evaluation	Post-treatment			As needed for trial data interpretation				
Scheduling Window (Days):		-28 to -1 days	1	W (± 7	eek days) ^b	Month 3 $\pm 7 \text{ days}^{c}$		(± 1	nth) (± 2 months)		s) 36	throughout and after the study period as determined by the Principal Investigator		
Administrative Procedures			_				,	_							
Informed Consent	X		Г	l	l		Ι	Г			Ι				I
LOH evaluation	X														
Tobacco and alcohol use history	X						X	X	X	X	X	X	X	X	
Prior oral cancer history	X														
Inclusion/Exclusion Criteria		X													
Demographics and Medical History		X													
Concomitant Medication Review		X													
Trial Treatment Administration			X	X	X	X									
Oral Cancer-free Survival Status															X
Clinical Procedures/Assessi	nents														•
Review Adverse Events		X		X	X	X	Xa								1
Physical Examination		X		X	X	X	X ^a X	X	X	X	X	X	X	X	1
ECOG Performance Status		X													
Laboratory Procedures/Ass	sessments: an	alysis perfo	rmed	l by l	LOC	AL la	boratory				•				
Pregnancy Test – Urine or Serum �-HCG		Xª					Xª								
Urinalysis		X					X ^a								
CBC with Differential		X		X	X	X	X	Xa		X					
Comprehensive Serum Chemistry Panel		X		X	X	X	X	Xa		X					
T3, FT4 and TSH		X					X ^a	Xª							
Non-invasive Efficacy Meas	surements						_								
Oral lesion measurement		X					X			X					
Tumor Biopsies/Archival T				4 30										 	 

Trial Period:	Screening Phase		Treatment Cycles ^a				Follow-Up							Long-Term Follow-Up	
Treatment Cycle/Title:	Fitle: Prescreening (Visit 1)		1	2	3	4	End of Treatment / Re-evaluation	Pos			ost-tro	eatme	nt	As needed for trial data interpretation	
Scheduling Window (Days):		-28 to -1 days	1	W (± 7 d	eek days 7) ^b	Month 3 ± 7 days ^c	(± 1 month)		month) (± 2 months)				s) 36	throughout and after the study period as determined by the Principal Investigator
Archival or Newly Obtained Tissue Collection ^d	X														
Newly Obtained Tissue Collection		Xe					X			X					
Correlative Studies Blood Collection ^f	X			X			X			X				X	
Oral Swab Collection ^f	X			X			X			X				X	

^a To be performed only in subjects randomized to the experimental arm. Pregnancy test must be performed <72 hours prior to the first dose of study medication.

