^b If there are treatment delays, timing of subsequent cycles will be adjusted so that pembrolizumab is given every 3 weeks (± 7 days)

^c In subjects who had a treatment delay, evaluation should be postponed until at least 2 weeks after last dose of treatment

^d At any time point after enrollment, any archival or newly obtained tissue as part of standard of care for monitoring of oral IEN or newly developed oral cancer may be collected for correlative studies. This applies to any subject participating in the study from the time of enrollment, regardless of LOH or randomization status.

^e During the screening phase, newly obtained tissue collection may be performed within 12 months before randomization

^f For patients diagnosed with oral cancer during the study, extra blood collection and oral swabs collection may be performed approximately at the time of diagnosis of invasive cancer.

NCT02882282

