7.1 TRIAL PROCEDURES

7.2 Trial Procedures

The Trial Flow Chart - Section 6.0 summarizes the trial procedures to be performed at each visit. Individual trial procedures are described in detail below. It may be necessary to perform these procedures at unscheduled time points if deemed clinically necessary by the investigator.

Furthermore, additional evaluations/testing may be deemed necessary by the IND Office and/or Merck for reasons related to subject safety. In some cases, such evaluation/testing may be potentially sensitive in nature (e.g., HIV, Hepatitis C, etc.), and thus local regulations may require that additional informed consent be obtained from the subject. In these cases, such evaluations/testing will be performed in accordance with those regulations.

Subjects found to be LOH negative, or subjects who are LOH positive but do not undergo randomization for any reason (including declining randomization) will not be removed from the study. However, they will only undergo the study procedures described under "Pre-Screening Visit 1" and "Long Term Follow-up" of the Trial Flow Chart - Section 6.0. Their medical care and follow up will be performed by the treating physicians according to institutional standards. All other subjects should follow the trial procedures according to the Trial Flow Chart - Section 6.0.

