7.3.1. Immediate Reporting Serious Adverse Events to Merck

A serious adverse event is any adverse event occurring at any dose or during any use of Merck's product that:

- Results in death;
- Is life threatening;
- Results in persistent or significant disability/incapacity;
- Results in or prolongs an existing inpatient hospitalization;
- Is a congenital anomaly/birth defect;
- Is a new cancer (that is not a condition of the study);
- Is associated with an overdose;
- Is another important medical event

Refer to Table 6 for additional details regarding each of the above criteria.

Any serious adverse event, or follow up to a serious adverse event, including death due to any cause other than progression of the cancer under study that occurs to any subject from the time the subject is randomized through 90 days following cessation of treatment, or the initiation of new anti-cancer therapy, whichever is earlier, whether or not related to Merck product, must be reported within 5 working days of knowledge of the event to the IND Office and within 2 working days to Merck Global Safety.

ECIs (both non-serious and serious adverse events) identified in this guidance document from the date of first dose through 90 days following cessation of treatment, or 30 days after the initiation of a new anticancer therapy, whichever is earlier, need to be reported within 24 hours to the IND Office and within 2 working days to Merck Global Safety(Attn: Worldwide Product Safety; [contact]), regardless of attribution to study treatment, consistent with standard SAE reporting guidelines.

Non-serious Events of Clinical Interest will be forwarded to Merck Global Safety and will be handled in the same manner as SAEs.

Additionally, any serious adverse event, considered by an investigator who is a qualified physician to be related to Merck product that is brought to the attention of the investigator at any time outside of the time period specified in the previous paragraph also must be reported immediately to the IND Office and to Merck.

All subjects with serious adverse events must be followed up for outcome.

Product: MK-3475

Protocol/Amendment No.:

Table 6 Evaluating Adverse Events

An investigator who is a qualified physician, will evaluate all adverse events as to:

V4.0 CTCAE Grading	Grade 1	Mild; asymptomatic or mid symptoms; clinical or diagnostic observations only; intervention not indicated.		

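### Periodic thyroid monitoring is suggested during treatment, but the flow chart schedules no thyroid test between screening and the month-3 visit after dose 4

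*Combined protocol and SAP*

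**What the plan says.** Section 5.6.1, under hyperthyroidism and hypothyroidism, states that thyroid disorders may arise at any point in treatment and tells sites to "Monitor patients for changes in thyroid function (at the start of treatment, periodically during treatment, and as indicated based on clinical evaluation". That is three separate elements: a baseline test, periodic tests on treatment, and tests prompted by clinical findings. The section introduces its content as guidance: "Suggested supportive care measures for the management of adverse events with potential immunologic etiology are outlined below and in greater detail in the ECI guidance". The guidance it points to is a separate manual.

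In the flow chart (section 6.2) the T3, FT4 and TSH row is marked at main study screening, at the month-3 end-of-treatment visit and at the first post-treatment visit. The last two apply to the experimental arm only. The cells for cycles 1 to 4 are empty. Blood count and chemistry are marked at cycles 2, 3 and 4, as is the row "Review Adverse Events". Table 5 (section 7.1.3) lists the thyroid hormones under other tests, outside the chemistry panel.

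The opening section of chapter 7 (7.2 Trial Procedures) makes the chart the working schedule for randomized patients: "All other subjects should follow the trial procedures according to the Trial Flow Chart - Section 6.0". It also leaves room for extra testing: "It may be necessary to perform these procedures at unscheduled time points if deemed clinically necessary by the investigator".

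**The concern.** The baseline element of section 5.6.1 has a scheduled test, and the clinically prompted element is covered by unscheduled testing. The periodic element has no scheduled test during the four doses. A site that follows the flow chart exactly will draw blood at cycles 2, 3 and 4 and will not request thyroid tests on it.

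At stake is the timing of detection in the pembrolizumab arm. An asymptomatic or non-specific thyroid disorder that begins early would be found at month 3 rather than during treatment, and one that resolved before month 3 might not be found at all. Safety and tolerability is the first secondary objective (section 3.3). The patients have premalignant disease, and section 4.2.4 argues for a favourable risk/benefit ratio in them, so a cheap gap in safety monitoring is worth closing.

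**Working it through.** **Schedule against guidance.** The thyroid row was read column by column and checked against its neighbours.

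| Row | Screening | C1 | C2 | C3 | C4 | Month 3 | First post-treatment visit |
|---|---|---|---|---|---|---|---|
| T3, FT4, TSH | X | – | – | – | – | X | X |
| Blood count | X | – | X | X | X | X | X |

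The blood count row has its marks at cycles 2 to 4 in the same extracted table, so the empty thyroid cells are unlikely to be a reading error. Scheduled thyroid tests from dose 1 to dose 4: none.

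**Length of the interval.** Inputs: four doses every 3 weeks (Table 2), and a month-3 visit with a window of 7 days either side (flow chart). The chart does not say from which day month 3 is counted; dose 1 is assumed here.

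- Dose 1 to dose 4: 3 × 21 = 63 days = 9 weeks.
- Month 3 as 12 weeks: 12 ± 1 = 11 to 13 weeks after dose 1.
- Month 3 as 13 weeks: 13 ± 1 = 12 to 14 weeks after dose 1.
- Combined: 11 to 14 weeks without a scheduled test, of which 9 are between the first and last dose and 2 to 5 (11 − 9 and 14 − 9) follow dose 4.
- Delays extend this. Footnote c of the chart reads: "In subjects who had a treatment delay, evaluation should be postponed until at least 2 weeks after last dose of treatment".

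**What a cycle-3 test would change.** Nominal cycle 3 is day 43, counting dose 1 as day 1. Month 3 falls between day 84 − 7 = 77 and day 91 + 7 = 98. A disorder already detectable at cycle 3 would be found 77 − 43 = 34 to 98 − 43 = 55 days earlier, about 5 to 8 weeks.

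**How many patients.** Inputs: 104 randomized 1:1 gives about 52 on pembrolizumab. The adverse-event table in section 4.2.4 reports treatment-related hypothyroidism in 34 of 495 lung cancer patients, 1 of them at Grade 3–5.

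- Any grade: 34/495 = 6.9%; 52 × 34/495 = 3.6 expected cases.
- Uncertainty in the rate alone (Clopper-Pearson 95%: 4.80% to 9.47%): 52 × 0.0480 = 2.5 to 52 × 0.0947 = 4.9.
- The observed count would vary more than that. At exactly 6.9%, the central 95% binomial range for 52 patients is 1 to 7.
- Grade 3–5: 52 × 1/495 = 0.1.

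Only cases that begin before cycle 3 could be found earlier by a cycle-3 test. The documents give no onset times, so that share cannot be calculated.

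**The case against.** The strongest defence is that nothing binding is broken. Section 5.6.1 offers suggestions, gives no interval for periodic testing, and defers detail to a manual that is not part of these documents and may itself set thyroid tests. Section 4.2.4 describes a three-month treatment period and the month-3 column is labelled end of treatment, so baseline plus end-of-course testing can be argued to be adequate for four doses. This softens the conflict without removing it. Section 5.6.1 lists periodic testing apart from clinically prompted testing, and a single test after the last dose is a weak reading of periodic monitoring during treatment.

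A reader might infer that thyroid disorders go unmonitored on treatment. The documents do not support that. Section 7.2.3 asks for an assessment for possible immune-related events before each dose, including laboratory review and questions about symptoms, with further tests if something is found. Examinations and adverse-event reviews are marked at cycles 2 to 4, and unscheduled tests are allowed. These safeguards should catch symptomatic cases. They depend on symptoms, or on a laboratory result that no scheduled draw produces, so asymptomatic change is what remains.

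A reader might also infer that dosing decisions would be wrong. Table 3 says of Grade 2–4 hypothyroidism: "Therapy with pembrolizumab can be continued while treatment for the thyroid disorder is instituted". It holds treatment for hyperthyroidism only from Grade 3. Table 6 describes Grade 1 events in terms of "clinical or diagnostic observations only; intervention not indicated".

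Nor do the documents show that the toxicity tables would be materially distorted. Section 7.2.1 usually leaves laboratory abnormalities out of the adverse-event record but requires those marked clinically significant to be recorded. A persistent abnormality would still be found at month 3 or the next visit. An asymptomatic one that resolved earlier could go unrecorded, but the number cannot be estimated.

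**Conclusion.** The point holds as a minor mismatch between the guidance and the schedule. No thyroid test is scheduled between screening and the month-3 visit, about 11 to 14 weeks after dose 1 and longer after delays, of which about 9 weeks are on treatment. The practical gap is mainly asymptomatic or non-specific thyroid change in the pembrolizumab arm.

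This rests on three assumptions: month 3 runs from dose 1, no dose is delayed, and the lung cancer rate carries over to this population and its four-dose course. The 3.6 expected cases describe how common hypothyroidism might be. They are not a count of patients who would be missed or who would gain from an extra test. That number is some unknown part of the 3.6, because onset times are not given. The separate guidance manual could narrow the gap if it specifies on-treatment testing. Dosing rules and the primary analysis of oral cancer-free survival are not affected.

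**What to change.** In the flow chart, mark T3, FT4 and TSH for the pembrolizumab arm at one on-treatment cycle, for example cycle 3, using the blood already drawn there for blood count and chemistry. The cost is one edited row and about 52 × 1 = 52 add-on assays, with no extra visit or procedure, plus follow-up of some abnormalities that prove transient.

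If the sponsor prefers not to test on treatment, section 5.6.1 should say that thyroid testing between screening and month 3 is prompted by clinical findings only, so that the text and the schedule agree. That costs one sentence but leaves asymptomatic change undetected until month 3.

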5.7 Diet/Activity/Other Considerations

5.7.1 Diet

Subjects should maintain a normal diet unless modifications are required to manage an AE such as diarrhea, nausea or vomiting.

5.7.2 Contraception

Pembrolizumab may have adverse effects on a fetus in utero. Furthermore, it is not known if pembrolizumab has transient adverse effects on the composition of sperm. Non-pregnant, non-breast-feeding women may be enrolled if they are willing to use 2 methods of birth

control or are considered highly unlikely to conceive. Highly unlikely to conceive is defined as 1) surgically sterilized, or 2) postmenopausal (a woman who is ≥45 years of age and has not had menses for greater than 1 year will be considered postmenopausal), or 3) not heterosexually active for the duration of the study. The two birth control methods can be either two barrier methods or a barrier method plus a hormonal method to prevent pregnancy. Subjects should use birth control for up to 120 days after the last dose of study therapy.

The following are considered adequate barrier methods of contraception: diaphragm, condom (by the partner), copper intrauterine device, sponge, or spermicide. Appropriate hormonal contraceptives will include any registered and marketed contraceptive agent that contains an estrogen and/or a progestational agent (including oral, subcutaneous, intrauterine, or intramuscular agents).

Subjects should be informed that taking the study medication may involve unknown risks to the fetus (unborn baby) if pregnancy were to occur during the study. In order to participate in the study they must adhere to the contraception requirement (described above) for the duration of the study and during the follow-up period defined in section 7.2.2-Reporting of Pregnancy and Lactation to the IND Office and to Merck. If there is any question that a subject will not reliably comply with the requirements for contraception, that subject should not be entered into the study.

